4.3. CRAFT-IMG

Primary endpoint:

- i. Alterations in imaging parameters between women with a full dilatation C-section in a previous pregnancy and either a cervix $\leq 25\text{mm}$ or a cervix $>25\text{mm}$ in this pregnancy which culminates in a preterm (<37 week) delivery.

5. Sample size and power calculation

All power calculations were performed by the trial statistician [name].

CRAFT-OBS: With estimated prevalence of 15% preterm birth rate prior to 37 weeks, and 16.2% of all deliveries being by emergency caesarean section; we will require data on 2200 women to estimate the event rate to 10% relative accuracy (e.g. 13.5% to 15.6%).

An average district general hospital has 4,000 deliveries per year, of which 648 (16.2%) might be by Emergency Caesarean. We aim to recruit 324 of these (50%) at a minimum of 7 study sites. At St Thomas' Hospital rather fewer deliveries (11%) are caesareans in labour; so we will aim for at least 20 sites, taking the assumptions above into account.

If we acquire data of cervical length and/or quantitative fetal fibronectin in this cohort, we will be able to validate these prediction tools. If we treat a short cervix of $\leq 25\text{mm}$, and a raised qfFN of $\geq 50\text{ng/ml}$ as positive tests, we anticipate a 75% sensitivity and 83% specificity from the literature for both tests (16).

Assuming 10% event rate, 1000 women (100 cases and 900 controls) would allow use to estimate the sensitivities of qfFN and CL to within 10% and the specificities to within 3% of the true value. The PPV would be estimated within 7% and NPV within 1.5% of their true values.

CRAFT-RCT: Pilot data indicates that at least 10% of all births and 70% of preterm births associated with FDCS occur before 34 weeks. In order to detect a reduction in this rate from 10% to 5% 474 women are required in each group to give 80% power. We will aim to recruit 500 in each arm in order to allow for 5% loss to follow-up.

CRAFT-IMG: We consider that the participation of 60 women in this sub-study will provide useful information for planning future research; this is achievable by recruiting at 2 sites (UCLH and St Thomas' Hospital): 30 women with cervix $>25\text{mm}$ and 30 women with cervix $\leq 25\text{mm}$ (15 women with cerclage, 15 women without).

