If we have data from participants in this study of their cervical length and/or quantitative fetal fibronectin we will be able to carry out predictive statistics. This would involve calculating ROC curves for prediction of spontaneous preterm birth for both fibronectin and transvaginal cervical

length measurement as a continuous variable, for delivery <24, <30, <34 and <37 weeks gestation. From the optimal thresholds, predictive statistics will be calculated.

6. Participant inclusion and exclusion criteria

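### Sensitivity at cut-offs picked as optimal on the study's own ROC curves will be overstated, and the plan neither defines the criterion nor corrects for the selection

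*Combined protocol and SAP*

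**What the plan says.** The last paragraph of Section 5 (Sample size and power calculation) is conditional: "If we have data from participants in this study of their cervical length and/or quantitative fetal fibronectin". Given such data, it plans ROC curves for both tests on their continuous scale, "for delivery <24, <30, <34 and <37 weeks gestation". Two tests and four gestations make up to eight curves. It ends: "From the optimal thresholds, predictive statistics will be calculated". Which criterion makes a threshold optimal is not said.

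Earlier in Section 5, fixed rules are named: a cervix of 25 mm or less and a qfFN of 50 ng/ml or more count as positive. For these, "we anticipate a 75% sensitivity and 83% specificity from the literature for both tests". With 100 cases and 900 controls the plan expects "to estimate the sensitivities of qfFN and CL to within 10% and the specificities to within 3% of the true value", and PPV and NPV to within 7% and 1.5%.

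Section 8 (Data analysis) mentions standard predictive statistics at <34 and <37 weeks for CRAFT-OBS. For CRAFT-RCT it mentions a statistic at 25 mm with the area under the curve, and validation of current tools. Section 4.1 lists predictive modelling of the two tests at <34 and <37 weeks as a secondary endpoint. No section describes a split sample, cross-validation, bootstrap correction or external data set.

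**The concern.** A cut-off that maximises apparent accuracy in a sample is partly fitted to the noise of that sample. Scored in the same women, it looks better than it would in new women. The effect falls on the quantity estimated from fewest people. Here that is sensitivity, because cases are few and controls many.

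The plan presents this work as validating existing tools in a group where their performance is unknown. Validation means scoring a rule fixed beforehand. If accuracy at re-tuned cut-offs is reported without correction beside accuracy at 25 mm and 50 ng/ml, the re-tuned cut-offs will tend to look superior even when they are not. The risk is greatest for the rarest outcomes, <24 and <30 weeks, which appear only in the Section 5 paragraph and not in the endpoint or analysis sections.

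**Working it through.** **1. The plan's own precision figures.** Inputs from Section 5: 100 cases, 900 controls, sensitivity 75%, specificity 83%. Expected counts are 75/100 true positives and 747/900 true negatives. Hence PPV = 75/(75 + 153) = 75/228 and NPV = 747/(747 + 25) = 747/772. Half-widths of the 95% interval, Wald formula 1.96 × √(p(1−p)/n):

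- sensitivity: 1.96 × √(0.75 × 0.25/100) = 8.5 points
- specificity: 1.96 × √(0.83 × 0.17/900) = 2.5 points
- PPV: 1.96 × √(0.329 × 0.671/228) = 6.1 points
- NPV: 1.96 × √(0.968 × 0.032/772) = 1.25 points

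The larger Clopper-Pearson half-widths are 9.7, 2.6, 6.5 and 1.5. The stated 10, 3, 7 and 1.5 therefore reproduce, for a cut-off fixed in advance.

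**2. Marker model (assumed).** For an equal-variance binormal marker, 75% and 83% give d′ = z(0.75) + z(0.83) = 0.674 + 0.954 = 1.63, and AUC = Φ(1.63/√2) = 0.875.

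**3. Case numbers.**

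- Section 5 directly: 100 in 1000.
- Section 5, 15% before 37 weeks in 2200 women, if all are tested: 0.15 × 2200 = 330.
- Section 1.1 rates: up to 20% of in-labour caesareans at full dilatation, with preterm rates of 13.5% against 2%. Then 0.2 × 13.5% + 0.8 × 2% = 4.3%, or 43 in 1000. Applying Section 5's 70% before 34 weeks (stated for full-dilatation caesareans only) gives 0.7 × 43 ≈ 30.
- For <24 and <30 weeks no rate is given. Ten cases in 1000 is an assumption for illustration.

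**4. Simulation.** In each replicate the cut-off is chosen in the sample. The bias is apparent sensitivity minus true sensitivity at that cut-off, averaged over 1500 or more replicates. Ranges in the Youden column at AUC 0.875 are the spread between repeat simulations.

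| Cases / women | Youden, AUC 0.875 | Closest to corner, AUC 0.875 | Youden, AUC 0.70 |
|---|---|---|---|
| 330 / 2200 | 1.4–1.5 | 1.1 | 2.0 |
| 100 / 1000 | 2.9–3.2 | 2.2 | 4.1 |
| 43 / 1000 | 5.2–5.4 | not run | not run |
| 30 / 1000 | 6.4–6.5 | 5.1 | 8.8 |
| 10 / 1000 (assumed) | 12.7–13.1 | 11.1 | 15.4 |

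Entries are percentage points. Specificity bias at AUC 0.875 is 0.3 points or less throughout. If the Section 1.1 rates hold and all 2200 women are tested, there are 95 cases before 37 weeks and 66 before 34; the Youden bias is then 3.2 and 4.0 points. Recording cervical length to 1 mm (SD 8 mm assumed) lowers the 100-case figure to 2.2.

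**5. Knock-on for PPV and NPV.** At 100/1000 with Youden, mean apparent sensitivity and specificity are 0.812 and 0.797, against true values of 0.783 and 0.793. At 10% prevalence:

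- PPV: 0.0812/(0.0812 + 0.9 × 0.203) = 30.8% apparent, 0.0783/(0.0783 + 0.9 × 0.207) = 29.6% true
- NPV: 0.7173/(0.7173 + 0.0188) = 97.4% apparent, 0.7137/(0.7137 + 0.0217) = 97.0% true

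**The case against.** The strongest reply is that the plan already contains the unbiased analysis. Section 5 defines positive tests by fixed cut-offs and sizes the validation on them, and Section 8 names 25 mm again. Statistics at those values carry no selection bias. This stands, and a reader who inferred that the plan has no real validation would go too far. What is missing is a ranking: nothing says which set of results is the main one. The 25 mm statistic in Section 8 is also listed under CRAFT-RCT, where Section 6.2 admits only women at or below that value.

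A reader might also infer that the precision figures are wrong. They are not; they belong to the fixed cut-offs and the plan does not claim them for the optimal ones.

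Looking for another cut-off is legitimate, since the lay and professional summaries say it is unknown whether 25 mm is right in these women. That supports keeping the analysis, not leaving it uncorrected.

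Finally, this is a secondary, data-dependent analysis that touches neither powered primary endpoint. At 100 cases the bias is about a third of the stated 10-point precision. That is fair, but the bias always runs in one direction and it grows as cases become fewer.

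**Conclusion.** The concern holds for the optimal-threshold statistics only. As written, the plan gives upward-biased sensitivity there: about 1.5 points with 330 cases in 2200, about 3 with the documented 100 in 1000, about 5 to 6.5 with 43 to 30 per 1000, and about 13 with 10. Specificity is essentially unaffected.

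These sizes rest on assumptions the documents do not state: a binormal marker with equal variances, one AUC for all four gestations, and the Youden rule. Other rules and AUCs move the 100-case figure between 2.2 and 4.1.

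It is tempting to say that the study will overstate sensitivity by 3 to 13 points at the case numbers it will have. The documents do not support that. Only 100 in 1000 is given for the predictive statistics; 330, 43 and 30 are derived, and 10 is assumed. With 330 cases the bias is below that range. The number of women tested is not fixed, because test data are collected only where available.

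The paragraph also follows directly on the CRAFT-IMG sample size, so which study it refers to is unclear. If it meant only those 60 women, 6 to 9 cases (10–15%, assumed) would give a bias of 11 to 18 points at AUC 0.875.

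**What to change.** 1. State that accuracy at the fixed cut-offs (25 mm and 50 ng/ml) is the main validation result. For cervical length, base it on CRAFT-OBS, which can include women on both sides of the cut-off.
2. Define the optimality criterion before analysis, and say which participants the ROC paragraph covers.
3. Label optimal-threshold results as exploratory. Correct them for optimism by bootstrap, re-selecting the cut-off in every resample. The correction matters mainly for sensitivity and for the PPV and NPV that follow from it.
4. Report the number of cases behind each curve, so that readers can judge the <24 and <30 week results.

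The cost is a little extra analysis and slightly less favourable reported sensitivity. Recruitment, data collection and the primary endpoints are unaffected.

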6.1. Inclusion and exclusion criteria for ALL CRAFT participants

Inclusion criteria:

- Pregnant women under 23⁺⁶ weeks gestation with a history of previous caesarean section in labour.
- Singleton pregnancy.
- Willing and able to give informed consent (with or without interpreter).

Exclusion criteria:

- Under 16 years of age.
- Inability to give informed consent.
- Previous caesarean section carried out before labour.
- Women who have been commenced on management with progesterone, a cerclage or arabin pessary as part of their care or another research study

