Primary objective	
 1. CRAFT-OBS: To assess the risk of preterm birth or late miscarriage in women following an in labour caesarean section 2. CRAFT-RCT: To assess if cervical cerclage reduces preterm birth in pregnant women with a short cervix following a previous in labour caesarean section 3. CRAFT-IMG: To assess if alterations in MRI parameters or ultrasound characteristics occurs in women who undergo a late miscarriage or preterm birth following an in labour caesarean section.
Trial Design	Prospective observational study, nested randomised controlled trial and imaging sub-study in a selected cohort
Endpoints	Incidence of preterm birth at < 34 weeks gestation
Sample Size	CRAFT-OBS: 2200 women, CRAFT-RCT: 1000 women, CRAFT-IMP: 60 women

Study Protocol: **Cerclage After Full-dilatation caesarean-section**

IRAS ID:261294

REC: REC 19/LO/1270

Version 2.0

Date: 10.09.19

Summary of eligibility criteria	CRAFT-OBS: pregnant women 14 ⁺⁰ -23 ⁺⁶ week with a previous history of caesarean section in labour. CRAFT-RCT: pregnant women with a previous history of caesarean section carried out at full dilatation and a short cervix ($\leq 25\text{mm}$) in current pregnancy. CRAFT-IMG: pregnant women with a previous history of caesarean section carried out at full dilatation (30 women with cervix $>25\text{mm}$; 30 CRAFT-RCT participants).
Maximum duration of treatment of participant	Until delivery or removal of cerclage at 37 weeks gestation
Version and date of final protocol	Version 2.0 (10/09/19)
Version and date of protocol amendments	To be inserted

[figure not shown]

Figure 1: Flow of participants through CRAFT project

STUDY SYNOPSIS.....	4
LAY SUMMARY.....	8
PROFESSIONAL SUMMARY	8
GLOSSARY OF TERMS	11
1. Introduction.....	12
1.1. Background.....	12
1.2. Rationale for study.....	13
Study aims and objectives	15
2.	
2.1. Aims.....	15
2.2. Study objectives	15
2.2.1. CRAFT-OBS: a study of risk and management in women with a history of CS in labour	15
2.2.2. CRAFT-RCT: a trial of USS indicated cerclage in women with history of FDCS	16
2.2.3. CRAFT-IMG: a sub-study evaluating imaging methods for assessing risk and management of women with a history of FDCS.....	16
3. Study Design	16
3.1. CRAFT-OBS.....	16
3.2. CRAFT-RCT	16
3.3. CRAFT-IMG	17
3.4. Expected study duration	17
4. Study Endpoints	17
4.1. CRAFT-OBS.....	17
4.2. CRAFT-RCT	18
4.3. CRAFT-IMG	18
5. Sample size and power calculation	19

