Over 25% of all deliveries in the UK are by CS and up to 20% of in labour caesarean sections occur at full dilatation, which could affect up to 20,000 women in the UK per annum (8). These women have a six-fold increased incidence of subsequent preterm birth compared with women who undergo CS in the first stage of labour (adjusted odds ratio 5.8; 95% confidence interval 1.08-30.8)(3); 13.5% in comparison with 2%. This equates to around 2500 women per year in the UK. In women who lose a pregnancy, more than half will also go on to experience recurrent pregnancy losses in spite of intervention, compared to 14% of women with a history of preterm birth without previous FDCS (relative risk 3.06 95% confidence interval 1.22-7.71)(9). The relative risk of PTB in women with a previous emergency CS earlier in labour is unknown, however it is thought to be a continuum of risk, i.e. the later in labour the CS is carried out, the higher the risk of PTB in future pregnancies.

A screening programme to assess for cervical shortening in women with a previous FDSC is due to be implemented as part of new NHS commissioning guidance(1) and the revised *Saving Babies Lives Care Bundle*(2). It is unknown whether transvaginal cervical length screening for a short cervix predicts outcome in this group and there is currently limited evidence to inform optimal management of these women. It is also unknown whether first-line interventions for short cervix $\leq 25\text{mm}$ (vaginally-placed cerclages inserted in the distal cervix during pregnancy), used in other high-risk groups of women, is effective in this cohort. Preliminary data indicates that these interventions may be less efficacious, likely due to the injury having occurred in the proximal cervix, above the cerclage. A small retrospective analysis indicated that of 19 women who had experienced a LM/PTB subsequent to a FDSC and who then had a cerclage in the 3rd pregnancy, 10 (53%) still delivered <30 weeks gestation in comparison with 3% of a high-risk control group, who also had a cervical cerclage in situ after a LM/PTB (n=154).

This study has been developed in collaboration with the Preterm Birth Studies PPI Group at St Thomas' Hospital. They have confirmed that this issue is of vital importance to them and they will be consulted on all study literature and future directions associated with this project.

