2.2. Study objectives

2.2.1. CRAFT-OBS: a study of risk and management in women with a history of CS in labour

- i. Determine the incidence of LM and PTB (prior to 37 weeks) in women with previous CS in labour stratified by cervical dilatation.

- ii. If ultrasound measured cervical length and quantitative fibronectin are carried out, this data will be collated and help evaluate the ability of these tests to determine risk of preterm birth in women with a history of in labour caesarean.

2.2.2. CRAFT-RCT: a trial of USS indicated cerclage in women with history of FDCS

- i. Determine if an ultrasound-indicated cervical cerclage is effective management in women with a history of FDCS and cervical shortening (<25 mm) in preventing LM or PTB <34 weeks gestation. Evaluate the impact of intervention on short-term fetal and neonatal outcomes, assessed as a composite of fetal and perinatal death and major morbidity.
- ii. Assess the impact of both management strategies (i.e. cerclage and observation) on health economic outcomes for mother and infant in terms of number of nights in hospital; cost data to hospital discharge/28 days post delivery.

2.2.3. CRAFT-IMG: a sub-study evaluating imaging methods for assessing risk and management of women with a history of FDCS

- i. Ascertain whether MRI or ultrasound (or a combination of the two) can accurately predict PTB when abnormalities are detected in the cervix.
- ii. Identify which women are most likely to benefit from intervention.

3. Study Design

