3.1. CRAFT-OBS

This is a multicentre prospective cohort observational study of 2200 pregnant women with a previous history of CS in labour who will be recruited following their booking or scanning visit (Appendix: participating sites). Women who have had a previous FDCS and who are found to have a CL \leq 25mm on transvaginal ultrasound will be offered recruitment to the CRAFT-RCT (see below). Women with a previous FDCS and a CL \geq 25mm may be invited to participate in CRAFT-IMG. If patients have a clinically indicated transvaginal cervical length or qfFN during their pregnancy, this information will also be collected.

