7.1. Identification of participants

CRAFT-OBS

We will recruit pregnant women who are booked for their delivery at participating centres who provide written informed consent to participate in the study and who meet the study eligibility criteria.

Women who have previously had an emergency caesarean in labour will be identified through their booking appointment or scan appointments by the direct care midwife, doctor, sonographer and approached with information about this observational study. Clinical midwives, doctors or sonographers will highlight eligible women to the research team. The research team will then be able to discuss the research with patients if they are eligible at the time of their first trimester or second trimester scan.

CRAFT-RCT

Women participating in CRAFT-OBS will be eligible for CRAFT-RCT if they are found to have a cervix ≤ 25 mm prior to 23⁺⁶ weeks gestation with a history of FDCS. Women with a previous full dilatation caesarean section will be identified by a member of the direct care team and referred for cervical surveillance as per new guidance (1,2). The research team will check relevant hospital records when patients are consented in order to confirm a previous full dilatation caesarean section occurred. If these records are not available for review the patients will be excluded. Eligible women will be informed about the trial by a doctor, sonographer or midwife if their transvaginal ultrasound confirms a short cervix (≤ 25 mm). Members of the research team

Study Protocol: **Cerclage After Full-dilatation caesarean-section**

IRAS ID:261294

REC: REC 19/LO/1270

Version 2.0

Date: 10.09.19

(midwives, doctors and scanning practitioners) can then discuss the research further and consent women.

- If a woman is randomised to a cervical cerclage, the procedure needs to take place within 7 days of diagnosis of cervical shortening and removed around 37 weeks gestation. She will also have regular scan surveillance in accordance with local protocols. Rescue cerclage can be offered in cases of cervical opening with exposed membranes as per local guidelines. Targeted admission for bedrest and steroids can also be offered as per clinician practice and local protocols.

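### The section 6.1 exclusion of women already on progesterone, cerclage or pessary also covers CRAFT-OBS, so a cohort meant to measure risk can lose higher-risk women

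*Combined protocol and SAP*

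**What the plan says.** The criterion stands in section 6.1, headed "Inclusion and exclusion criteria for ALL CRAFT participants". It excludes "Women who have been commenced on management with progesterone, a cerclage or arabin pessary as part of their care or another research study". CRAFT-OBS has no list of its own, and nothing in sections 6.2 or 6.3 readmits treated women.

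The synopsis gives the CRAFT-OBS objective as "To assess the risk of preterm birth or late miscarriage in women following an in labour caesarean section". Section 2.2.1 makes it specific: "Determine the incidence of LM and PTB (prior to 37 weeks) in women with previous CS in labour stratified by cervical dilatation".

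On timing, section 6.1 admits women up to 23+6 weeks. Section 3.1 describes women "who will be recruited following their booking or scanning visit", and section 7.1 lets the research team "discuss the research with patients if they are eligible at the time of their first trimester or second trimester scan". The synopsis gives a lower limit of 14+0 for CRAFT-OBS, which section 6.1 does not repeat.

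Section 7.3 records cerclage and other pregnancy interventions after consent. Women who decline the RCT stay in the observational study and are managed locally. Section 8 plans no log of women excluded for prior treatment, no outcome data on them and no sensitivity analysis.

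**The concern.** The criterion suits a trial that randomises untreated women. In a cohort that estimates risk it works differently, because starting one of these treatments is usually a response to apparent risk, such as a previous loss or a short cervix. Excluding on it means selecting on a marker of the outcome.

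Nor does the rule produce an untreated cohort. Take two women who are both treated at 16 weeks. The one approached at her first-trimester scan is in, and stays in. The one first approached at her second-trimester scan is out. Membership then depends on local timing and practice. If the 14+0 lower limit governs, anyone treated before 14 weeks is always out.

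At stake are the overall incidence and the gradient by dilatation, which is the first aim in section 2.1. The gradient would be flattened if women with a previous full-dilatation caesarean (FDCS) were removed more often than the 4-9 cm group. A larger sample does not reduce this kind of error.

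**Working it through.** **Inputs from the documents**
- Section 5: CRAFT-OBS rate of delivery before 37 weeks 15%, n = 2200, 10% relative accuracy, so ±1.5 points. (The printed example range ends at 15.6%; 15% plus a tenth of itself is 16.5%.)
- Section 1.1: LM/PTB after FDCS 13.5%; up to 20% of in-labour caesareans are at full dilatation.
- Section 1.1: of 19 women with a loss or preterm birth after FDCS who then had a cerclage, "10 (53%) still delivered <30 weeks gestation in comparison with 3% of a high-risk control group". The exact 95% interval for 10/19 runs from 29% to 76%.

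**Assumed, because the documents do not say**
- f, the share of eligible women excluded for prior treatment.
- r, the risk in those women. I use 30% (near the lower limit above) to 53%.
- A two-sided 95% confidence level.

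**Step 1. The plan's own figure.** n = 1.96² × 0.15 × 0.85 / 0.015² = 2177, which agrees with 2200. The half-width at 2200 is 1.49 points.

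**Step 2. Effect of the exclusion.** Observed rate = (p − f·r)/(1 − f). It falls below p when r > p, is unchanged when r = p, and rises when r < p. With p = 15%, f = 5% and r = 10%, it is (0.15 − 0.005)/0.95 = 15.3%.

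**Step 3. Share needed to exceed 1.5 points in the whole cohort.** Solving for f gives f = 0.015/(r − 0.15 + 0.015).

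| r | f |
|---|---|
| 30% | 0.015/0.165 = 9.1% |
| 40% | 0.015/0.265 = 5.7% |
| 53% | 0.015/0.395 = 3.8% |

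These are shares of all eligible women, not of the FDCS stratum.

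**Step 4. Loss confined to the FDCS stratum, effect on the whole cohort.** If FDCS women are 20% of the cohort and 5% of them are excluded, f = 0.20 × 0.05 = 1%.
- r = 53%: (0.15 − 0.0053)/0.99 = 14.6%, a shift of 0.4 points.
- r = 100%, as a bound: 0.14/0.99 = 14.1%, a shift of 0.9 points.
- If instead the 1000 RCT women are counted within the 2200, FDCS women are at least 1000/2200 = 45%. Then f = 2.3%, and r = 53% gives 14.1%, again a shift of 0.9 points.

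**Step 5. Effect within the FDCS stratum.** With p = 13.5% and r = 53%:
- f = 5%: (0.135 − 0.0265)/0.95 = 11.4%, a shift of 2.1 points.
- f = 10%: (0.135 − 0.053)/0.90 = 9.1%, a shift of 4.4 points.

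With r = 30% and f = 5% the rate is (0.135 − 0.015)/0.95 = 12.6%, a shift of 0.9 points. The documents claim no precision for this stratum. With 20% of 2200 = 440 women, the 95% half-width is 1.96 × √(0.135 × 0.865/440) = 3.2 points.

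**The case against.** Several facts limit the effect, and they stand.

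- **The excluded share may be small.** The lay summary says cerclage for a short cervix after FDCS is not routine care. Women can be identified from booking, and section 7.3 describes consent before FDCS participants are referred for surveillance. How often approach comes late is unknown.
- **The 53% is an extreme input.** It comes from 19 women who had already had a loss or preterm birth after FDCS, and it counts deliveries before 30 weeks, not before 37. It need not apply to women treated only for a short cervix. Section 5 plans the RCT on 10% before 34 weeks, with 70% of preterm births before 34 weeks, so 10/0.70 = 14.3% before 37. That rate is drawn from FDCS births generally and may be low for a short cervix. With r = 14.3% and f = 5%, 13.5% becomes 13.46%, which is practically no change.
- **Uneven removal is not settled.** Section 7.3 refers only FDCS women to a surveillance clinic, but the professional summary says all women with a previous in-labour caesarean will be screened by transvaginal ultrasound.
- **Restricting to women untreated at entry is a legitimate target.** Including treated women does not recover untreated risk, and it complicates validation of cervical length (CL) and fetal fibronectin (fFN).

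A reader might infer that excluding 5% of FDCS women already exceeds the plan's 10% relative precision. The documents do not support this: that precision belongs to the whole cohort at 15%. A 2.1-point shift in an FDCS stratum of 440 lies inside its 3.2-point half-width, and the matching whole-cohort shift is 0.4 points.

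None of this explains why an RCT criterion governs the observational cohort, or why women treated soon after enrolment are kept while those treated just before are lost unrecorded.

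**Conclusion.** The point holds as a conditional one. Section 6.1 applies the exclusion to CRAFT-OBS, and the resulting cohort is neither untreated nor representative of all women with a previous in-labour caesarean. The bias is downward if the excluded women's risk exceeds the cohort average. The 19-woman series makes that plausible for women with a previous loss but does not establish it for all treated women. Flattening of the dilatation gradient is possible, not shown.

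The size cannot be determined from the documents. For the overall rate to move by more than the planned 1.5 points, between about 4% (risk 53%) and 9% (risk 30%) of all eligible women would have to be excluded. Larger shifts within the FDCS stratum need both a high excluded share and a risk near 53%. The case for acting rests on the mismatch between rule and objective, and on the absence of any record that would reveal the bias.

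**What to change.** 1. Take the prior-treatment criterion out of section 6.1 and place it in sections 6.2 and 6.3. Word the 6.3 version so that cerclage allocated by CRAFT-RCT does not exclude, since sections 3.3 and 7.1 plan 15 such women in CRAFT-IMG.
2. Enrol treated women in CRAFT-OBS, recording type, indication and start date of treatment. Section 7.3 already collects interventions.
3. In section 8, report incidence by dilatation in all women as the main figure, and again in women untreated at enrolment. Use the restricted set for CL and fFN validation.

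The cost is an amendment to one eligibility line, a few data fields and one further analysis, with no added procedure for participants. The downside is that the main figure becomes risk under current care, including some treated women. The restricted analysis addresses this by keeping the estimate in women untreated at entry.
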